NCT04060212

Microbial mechanisms of methylmercury metabolism in humans.

[name].

**Department of Environmental Medicine
[name]**

1. Background and Purpose of study.

1 A. Application Background. This submission seeks approval of a new study that follows essentially the same protocol of two prior approved studies we have conducted, with a modification that includes an additional intervention of administration of a prebiotic to influence change in the gut microbiota. The prior studies were #RSRB00050613 entitled Methylmercury metabolism and elimination in humans and #RSRB00057934 entitled Determination of methylmercury metabolism and elimination status in humans.

1 B. Purpose of the study.

The overall objective of this study is to investigate the role of gut microbes in mediating how humans metabolize and excrete the environmental neurotoxicant methylmercury (MeHg). Our secondary objectives are: 1) to derive non-invasive tools to evaluate an individual's MeHg metabolizing potential, 2) to identify dietary supplement approaches to enhance an individual's capacity to metabolize and excrete toxic MeHg, 3) to discover symbiotic bacterial strains with probiotic potential. Successful completion of the study Aims will eventually lead to advanced methodologies to better assess the risks of Me Hg on human health and identify factors that mitigate this risk.

1 C. Scientific Background.

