participants in the consent form) within the course of approximately 10 months and separated by an intermediate “washout” period of 4 months (Figure 1). Subject will not be required to refrain from fish or seafood during this washout period. Prior to the second trial subjects will receive a commercially available over the counter prebiotic (Prebiotin™) to be orally self-administered on a regular schedule for the entire trial 2 period. This prebiotic is not the subject of this investigation in this study, and is simply selected for its known effects of shifting gut microbial composition to enrich for healthier strains of bacteria (e.g. Bifidobacteria). Fecal sampling prior to and subsequent to prebiotic will be used to document changes in the microbiota for each individual. The prediction is that prebiotic induced change in the gut microbiota will result in a change in MeHg metabolism kinetics in each

individual.

2B. Rationale for Study Design

The main rationale for this study design is based on our evidence that de-methylation of MeHg in the human gut is the driving force for faster elimination MeHg that comes with eating fish. We therefore predict that with the methods we now have available to measure MeHg kinetics, coupled that with high-resolution analyses of gut microbiome characteristics in individual people who have undergone a controlled exposure to MeHg, we can resolve a microbial basis for MeHg metabolism in humans. This is an ambitious undertaking, and hence, is designed as a consortium project to be executed by three investigators with respective expertise in 1) human MeHg kinetics, 2) mouse microbiome manipulations and 3) microbial metagenomics and culturing methods. By design, the human subject component of the study is to be carried out at URMC. The objective is to capture “slow” and “fast” MeHg metabolizing human microbiome samples, that can be handed off to colleagues at MSU for specialized analyses that do not involve the human subjects, simply their de-identified samples.

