11. DATA ANALYSIS AND MONITORING

Sample Size Determination

We will target 40 participants (20 women, 20 men)for the reason that some statistical power is expected while we also are aiming to keep the study size appropriate for the logistics of recruiting and retention of subjects for both trials. We aim to recruit and consent 46 participant (23 women, 23 men) in anticipation of some drop out. A

complete cohort of 20 women and 20 men will afford the opportunity to assess sex-based differences. We have performed power analysis on the pairwise correlations between k_{el} and MeHg demethylation rate and/or bacterial taxa abundance. With grouped sexes, 40 subjects will have at least 80% power to detect a linear relationship where 19% or more of the variance in elimination rate is explained by de-methylation status or particular bacterial species abundance.

Planned Statistical Analysis

Relationships of taxa abundance with kinetic parameters of MeHg elimination rate (k_{el}), biotransformation in vivo (B_{vivo} , %iHg in feces) and in vitro (B_{vitro} , %MeHg biotransformation in cultures) will be evaluated. A total of 117 numerical values for k_{el} and B_{vivo} , B_{vitro} will be available (37 from our prior study and 40 subjects X 2 trials in the present study). Evaluation of slopes and R^2 values for elimination rate calculations in the prior study demonstrates that a difference of two days in MeHg half-life between two subjects can be determined with significance. Pairwise t-tests will be used to assess significance among pre- vs. post-prebiotic elimination rates (Aim1). The correlation between the (k_{el}) and biotransformation (B_{vivo} and B_{vitro}) will be evaluated for the 40 X 2 = 80 new human subject determinations in Aim 1. Graphical and numerical diagnostics will be used to test the linearity of the relationships and the homogeneity of variance. If these conditions are met, linear regression will be used to estimate functions for predicting k_{el} from B_{vivo} or B_{vitro} . The R system for statistical computing will be used throughout [26].

Data and Safety Monitoring.

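### The k_el versus B correlation and regression use 80 values, two per person, with no allowance for the pairing; if both measures are positively correlated within person, standard errors and p-values are too small

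*Combined protocol and SAP*

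**What the plan says.** Section 11, Planned Statistical Analysis, states that the correlation of k_el with B_vivo and B_vitro "will be evaluated for the 40 X 2 = 80 new human subject determinations in Aim 1". Before regression, "Graphical and numerical diagnostics will be used to test the linearity of the relationships and the homogeneity of variance"; if those two conditions hold, "linear regression will be used to estimate functions for predicting" k_el from either B measure. Independence of the values is not among the checks. No subject term, trial term, clustered error or repeated-measures method is named there, and Sections 2A and 5B speak only of statistical correlations.

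The same section does recognise the pairing for another question: "Pairwise t-tests will be used to assess significance among pre- vs. post-prebiotic elimination rates". Under Sample Size Determination, power is counted in people: "40 subjects will have at least 80% power to detect a linear relationship" explaining at least 19% of the variance in elimination rate.

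Sections 2A and 5C fix the order. Trial 1 is without prebiotic. In Trial 2 it is taken from a week before the first fish meal to the end.

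**The concern.** Eighty values from 40 people carry the information of 80 independent values only if at least one of the two variables is uncorrelated within person. Otherwise the usual regression standard error is too small, and tests and intervals for the slope or correlation overstate the evidence. The checks that the plan lists would not reveal this.

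This relationship is the one on which the study is powered. The prediction function also bears on the first secondary objective, "to derive non-invasive tools to evaluate" a person's metabolizing potential. Section 2A further predicts that "prebiotic induced change in the gut microbiota will result in a change in MeHg metabolism kinetics", without giving a direction or size. The second value of each pair may therefore differ systematically from the first, and it needs to be settled whether that disturbs a pooled fit.

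**Working it through.** **Inputs.** From Section 11: 40 subjects, 2 values each, R² = 0.19 (r = √0.19 = 0.436), power at least 80%. Not in the documents, so assumed: two-sided alpha 0.05, the ICCs of k_el and B, and any Trial 2 shift. Variables are scaled to SD 1 within a trial. Simulations used 40 subjects × 2, mostly 40,000 data sets per setting.

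**1. The plan's own power figure.** By Fisher z, power = Φ(atanh(0.436) × √(40 − 3) − 1.96) = Φ(0.467 × 6.083 − 1.96) = Φ(0.88) = 81%. The statement reproduces with 40 people as the unit. At 80% power the detectable R² is 0.185 with 40 independent units. It would be 0.095 with 80, which the plan does not claim.

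**2. Effect of ignoring the pairing, no shift between trials.** With two values per person and no true association, the true slope SD exceeds the reported standard error by √(1 + ICC_k × ICC_B). A nominal 5% test then rejects with probability 2 × [1 − Φ(1.96 / √(1 + ICC_k × ICC_B))]. For equal ICCs:

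| ICC (both) | SE factor | Effective values, 80/(1 + ICC²) | Rejection, formula | Rejection, simulated | 95% slope interval coverage at R² 0.19 |
|---|---|---|---|---|---|
| 0 | 1.00 | 80 | 5.0% | 5.0% | 95.0% |
| 0.3 | 1.04 | 73 | 6.0% | 6.2% | 94.0% |
| 0.5 | 1.12 | 64 | 8.0% | 7.9% | 92.0% |
| 0.6 | 1.17 | 59 | 9.3% | 9.2% | 90.8% |
| 0.8 | 1.28 | 49 | 12.6% | 12.8% | 87.1% |

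At ICC 0.5 the pooled fit reports a standard error of 0.113; 0.113 × 1.12 = 0.127, and simulation gives 0.127 to 0.128. If either ICC is 0 the factor is √1 = 1 and simulated rejection is 5.0–5.1%. With ICCs of 0.3 and 0.8 the factor is √1.24 = 1.11 and rejection is 7.9–8.0%.

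**3. Prediction, no shift.** The slope is unbiased, and pooled 95% prediction intervals for a new person cover 94.5–95.0%.

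**4. A shift d in Trial 2.** Three hypothetical cases:

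- *Both variables shift by d, with no link within a trial.* The shift adds d²/4 to the covariance and to each variance, so the pooled correlation is (d²/4)/(1 + d²/4): 0.0625/1.0625 = 0.06 at 0.5 SD and 0.25/1.25 = 0.20 at 1 SD. At ICC 0.5, simulated rejection is about 10% and 45%. At 0.3 SD it is 8.1%, so almost nothing is added to the 7.9% without a shift.
- *k_el alone shifts.* No false association arises, but the pooled line lies midway between the trials. It is off by d/2 for a person not on prebiotic: 0.25 SD at d = 0.5 and 0.50 SD at d = 1.
- *B shifts, and k_el shifts only through B* (R² 0.19, ICC 0.5). k_el then moves by 0.436 × d, that is 0.22 or 0.44 SD. The pooled slope stays at 0.436–0.438 and the off-prebiotic intercept is within 0.002 SD of the truth. Adding a trial term removes no bias and raises the slope SD from 0.109 to 0.116 (d = 0.5) or from 0.096 to 0.115 (d = 1).

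**The case against.** Section 11 attaches no alpha, p-value or interval to this correlation. The only significance test named beside it is the paired t-test, which respects the design. The stated use is prediction, where pairing alone does almost no harm. Inflation needs positive ICCs in both variables, and Section 1D reports that kinetics vary considerably within a person over time, so a low ICC is plausible. Section 3C calls the study a pilot.

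Much of this stands, and it limits the size of the point. It does not remove it. A relationship that is powered for detection will be tested, and the default test on 80 values is the pooled one. Section 1D's hypothesis of differences between individuals makes some within-person correlation reasonable, though its size is unknown.

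A reader might infer more than the documents support:

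- *That 80 values are used to claim power.* They are not; power rests on 40 people and reproduces.
- *That the plan declares the values independent or excludes an adjustment.* It is silent.
- *That the 117 values, which add the prior study, are wrongly analysed.* No model is named for them.
- *That a trial term must be in the main model because the prebiotic contaminates the pooled slope.* Section 2B treats demethylation as what drives elimination, and Section 1D expects the responsible microbes to respond to supplementation. Section 11 lists B with k_el among the kinetic parameters. That premise is the third case in step 4, where the pooled fit is unbiased and the trial term only costs precision. The other two cases are possible but depart from it.

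**Conclusion.** The point holds and should be fixed, at modest weight. It is certain that Section 11 does not say how two values per person are handled in the k_el versus B analysis. The consequence is conditional: rejection of roughly 6% to 13% in place of 5%, and slope interval coverage of 94% down to 87%, for equal ICCs of 0.3 to 0.8. There is no effect if either ICC is 0. These figures assume no trial shift and a two-sided 5% level.

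Whether the fixed trial order also matters depends on how the prebiotic acts, which the documents leave open. That is reason to report sensitivity analyses, not to require a trial term in the main model.

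**What to change.** Keep the correlation and regression, and add to Section 11:

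> Tests and confidence intervals for the k_el–B slope and correlation on the 80 new determinations will account for two determinations per subject, using subject-clustered standard errors with a small-sample correction (CR2 with Satterthwaite degrees of freedom). As sensitivity analyses, the same model with a fixed trial term and a fit to Trial 1 alone will be reported, with the mean Trial 1 to Trial 2 changes in k_el and in B beside them.

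One mean per subject (n = 40) is an acceptable alternative; it rejects 5.0–5.1% under the null. So is a random subject intercept, best kept for when between-person and within-person slopes are alike. With an overall slope of 0.30 and unequal component slopes (0.6 and 0, or 0 and 0.6), it gave 0.22 or 0.44.

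**Cost.** A wording change and a few lines of R, with no new data.

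- Slope intervals become about 1.05, 1.09, 1.18 and 1.36 times wider at ICC 0, 0.3, 0.5 and 0.8. Power at R² 0.19 is still 86–98%. Both were computed with a trial term; omitting it changes them little.
- The correction must be named. Across the null settings with a trial term, uncorrected clustered errors reject 7.1–8.0% and CR2 rejects 4.8–5.3%.
- The trial term cannot separate prebiotic from trial order, and it takes out of the slope any joint shift that may be part of the hypothesised effect. This is why the mean changes belong beside it.
- The Trial 1-only fit has 40 values and is less precise.

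### The regression predicting k_el from fecal biotransformation has no planned individual-level prediction error or out-of-sample check, although secondary objective 1 seeks tools for the individual

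*Combined protocol and SAP*

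**What the plan says.** Section 1B gives as the first secondary objective "to derive non-invasive tools to evaluate an individual" with respect to MeHg metabolizing potential. Section 1C explains the use: recognising fast and slow metabolizers in advance, with half-lives reported from under 30 to over 120 days.

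Section 11 (Planned Statistical Analysis) correlates k_el with B_vivo and B_vitro in the 80 new determinations (40 subjects in two trials, the second on prebiotic). It checks linearity and homogeneity of variance and continues: "If these conditions are met, linear regression will be used to estimate functions for predicting" k_el from either fecal measure. Nothing further is specified for that equation. The 37 values from the prior study are counted in a pool of 117, but are given no role in testing it.

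Section 11 (Sample Size Determination) states "at least 80% power to detect a linear relationship where 19% or more of the variance in elimination rate" is explained by demethylation status or by the abundance of a bacterial species.

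**The concern.** A slope that differs from zero shows that two quantities move together on average. It does not show how close the predicted half-life of one new person will be to the true one. The plan has the first kind of evidence and no measure of the second: no prediction error, no individual interval, no cross-validation or hold-out, no definition of fast and slow. Aim 2 tests the microbiome's role in mice, not this equation.

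The data structure adds a difficulty. Each person contributes two values, and the second is taken under a supplement that the protocol predicts will change kinetics. Residuals from a fit to all 80 are therefore not a clean guide to error in a new, unsupplemented person.

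At stake is what may be said about individual prediction at the end. As written, a strong and a weak equation could be reported in the same terms.

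**Working it through.** **Inputs from the documents.** n = 40 subjects; power at least 80%; R² = 0.19 or more (Section 11, Sample Size Determination); 80 new and 37 prior determinations (Section 11, Planned Statistical Analysis); half-life from under 30 to over 120 days (Section 1C).

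**Assumptions, because the documents are silent.** Two-sided alpha 0.05; bivariate normality; fast/slow divided at the median; SD of k_el equal to one quarter or one sixth of the 30–120 day range on the k_el scale.

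**1. The plan's own figure.** r = √0.19 = 0.436. By Fisher z, power = Φ(atanh(0.436) × √37 − 1.96) = Φ(0.4671 × 6.083 − 1.96) = Φ(0.88) = 81.1%. The stated 80% reproduces.

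**2. Gain in precision at R² = 0.19.** Residual SD / total SD = √(1 − 0.19) = 0.90, a reduction of 10%. This needs no value for the SD of k_el.

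**3. Fast/slow placement.** Median-split agreement = 0.5 + asin(r)/π.

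- R² = 0.19: 0.5 + 0.451/3.1416 = 64.4%, against 50% by chance. Simulated AUC is 0.70.
- By tertile (simulation): 52% of truly fast subjects are predicted fast and 16% are predicted slow.
- Extremes only (simulation): AUC is 0.77 for top versus bottom tertile and 0.80 for top versus bottom quartile.
- Larger R²: 68.5% at 0.30, 71.8% at 0.40, 75% at 0.50. For 80% agreement, R² = sin²(0.3π) = 0.65.

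**4. Individual interval in days.** k = ln2 / half-life, so 30 and 120 days give 0.02310 and 0.00578 per day: midpoint 0.01444, range 0.01733. The limits are for a subject at the midpoint, converted back by ln2/k. The last column uses t(38) = 2.024 and the factor √(1 + 1/40) = 1.0124.

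| Range taken as | SD of k_el | No predictor, ±1.96 SD | R² = 0.19, ±1.96 × 0.9 SD | R² = 0.19, ±2.024 × 0.9 SD × 1.0124 |
|---|---|---|---|---|
| 4 SD | 0.00433 | 30–117 days | 31–102 days | 31–107 days |
| 6 SD | 0.00289 | 34–79 days | 35–74 days | 35–76 days |

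In the last column the interval covers 92% (4 SD) or 61% (6 SD) of the 30–120 day range on the k_el scale.

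**5. How weak a significant slope can be.** With n = 40, p < 0.05 is reached at an observed r of 0.312 (R² = 0.097). A true R² of that size gives about 60% median-split agreement. If the 80 values were treated as independent, the threshold would be R² = 0.048, or about 57%.

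**6. Cost of judging the fit on its own data.** Simulation at true R² = 0.19 with one predictor:

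- n = 40: mean apparent R² 0.204, in new subjects 0.147; difference 0.057.
- n = 80, taken as independent: 0.196 and 0.169; difference 0.027.
- n = 40, significant fits only: 0.236 and 0.153; difference 0.083.

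Across all fits the optimism is about 0.03 to 0.06 in R². That is modest beside the lack of any individual-level measure.

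**The case against.** Four points can be made for the plan.

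- **Objective 1 is not tied to this equation.** Section 1B speaks of tools in the plural, and Section 1C already presents hair and fecal sampling as non-invasive. A reader might infer that the objective would be declared met on a fitted slope; no section says so. This stands. The inference that the equation is meant as a tool remains reasonable, because it is the only function for predicting elimination rate in the analysis plan.
- **R² = 0.19 is a detection floor.** The wording is "19% or more of the variance in elimination rate is explained by de-methylation status or particular bacterial species abundance". Section 2B regards demethylation as what drives faster elimination, so the sponsor may expect more. This stands, and the figures above describe the floor only. It does not remove the gap, since the plan would not measure individual accuracy at a higher R² either.
- **Weak is not useless.** A reader might infer that at this effect size the equation cannot tell fast from slow. The figures do not support that: 64% against 50%, and an AUC of 0.80 between extreme quartiles.
- **This is early work.** Section 3C calls the study a pilot and its main objective is mechanistic, so formal validation of a tool could come later. That is a fair argument against demanding a pass mark now. It is not an argument against reporting the error of an equation described as predictive.

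A reader might also infer that overfitting is the main fault, or that the equation is judged by its fit. With one predictor the optimism is small, and the plan names no performance measure for the equation, not even R².

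**Conclusion.** The concern holds in a limited form. Section 11 plans a predictive equation without any measure of how well it predicts for one person, and without a subject-level or external check.

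At the smallest detectable effect, discrimination would be weak: residual SD down 10%, about 64% correct at a median split, AUC about 0.70. These results rest on bivariate normality and, for the 64%, on the median as the cut. The interval in days also depends on an SD that the documents do not give. A reader might infer that individual error spans nearly the whole human range; that follows under the 4 SD assumption (92%) but not under 6 SD (61%).

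The documents do not support saying that the tool would fail, since the true R² may be well above 0.19. They support saying that the plan, as written, would not show whether it works for an individual.

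**What to change.** Add to Section 11, Planned Statistical Analysis:

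1. Report leave-one-subject-out prediction error for each equation, removing both determinations of a person together, in days of half-life. Give an individual 95% prediction interval and the share correctly placed as fast or slow, with the cut stated in advance.
2. If the 37 prior values come from different people and their fecal measures are comparable, fit the equation on one data set and test it unchanged on the other, using the 40 Trial 1 (no-prebiotic) values from this study. The documents settle neither condition, so the sponsor should confirm both first.
3. Describe the result as an association unless this out-of-sample performance supports individual prediction. No numerical pass mark is asked for, since the documents offer no basis for one.

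The cost is a few lines of R and a short addition to the text, with no new subjects, samples or visits. The downside is that the claim about individual prediction may become less favourable.
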